3. SCHEDULE OF EVALUATIONS

Visit Number	Screen	Visit 1	Contacts 1 and 2	Visit 2	Visit 3	Visit 4	Visit 5	Visit 6	Contact 3
Trial Timeline	Day -21 to 0	Day 0	Days 1 and 2 ¹	Day 3	Day 7	Day 42	Day 180 ¹	Day 360 ¹	Days 720 ¹
Visit/Contact Window (Days)	N/A	N/A	+/- 0	+/- 1	+/- 1	+/- 4	+/- 28	+/- 28	+/- 28
Informed Consent	X								
Inclusion/Exclusion	X	X							
Medical History	X								
Interim Medical History		X	X	X	X	X	X	X	X
Concomitant Medications	X	X	X	X	X	X	X	X	
Physical Examination	X								
HIV and Illicit Drug Test	X								
Physical Assessment: Vital Signs ² /Node Check		X		X	X	X	X	X	
Safety Labs (CBC, Blood Chemistry, PT, PTT, Urinalysis) ^{2,3}	X	X			X	X			
Surgical Treatment		X							
Surveillance (30 minutes)		X							
CT	X	X				X	X	X	
Diary Cards Distributed/Collected		X			X	X	X	X	X
Unsolicited Adverse Events		X	X	X	X	X	X	X	X

¹ Subjects will be contacted at Days 1 and 2, Days 42 and at 6 months, 1 year, and 2 years with a scripted telephone contact for safety follow-up and scheduling.

² Vital signs and laboratory values will be evaluated using the appropriate FDA draft guidance.

³ Any abnormal laboratory result arising post-administration, and of moderate or greater severity, will be followed until results return to baseline value or for the duration of safety follow-up.

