- d. Verify telephone contact information and mailing address and provide instructions to participant in the event of a change in contact information.

Additional Clinic Visits

Any subject with an abnormal laboratory result or who experiences an adverse event may be requested to come into the clinic for additional follow-up evaluation not specified by the protocol if this is deemed medically prudent by the investigator.

9.2 *Obtaining, Handling, Storage, and Shipment of Specimens*

9.2.1 *Blood Samples for Safety Laboratory Tests*

Blood samples collected for safety analysis will be labeled and handled per the local reference laboratory standard operating procedures for hematology and biochemistry profiles. Blood samples for safety laboratory tests will include one 5 mL and one 10 mL sample, as well as one 4 mL sample for PT and PTT testing where specified.

9.2.2 *Urine Samples*

A clean-catch urine sample will be collected by each participant for safety evaluation. Study personnel will be responsible for instructing subjects on this technique. Urine samples will be handled and labeled per the local reference laboratory standard operating procedures for urinalysis.

9.3 *Safety Data Review*

The SRC will perform a review of the safety data through seven days post-administration for the first three subjects, and through seven days post-administration for all subsequent subjects. The SRC will use the following evaluation criteria to approve the completion of enrollment after the first 3 subjects:

- a) Absence of SAEs or severe AEs "definitely", "probably" or "possibly" related to the experimental device.
- b) No evidence of severe hematologic or biochemical toxicity.
- c) No consistent pattern of AEs that, in the judgment of the SRC, represents a significant threat to the safety of the subjects with continued enrollment.

Approval from Agenta will be obtained before proceeding with treatment of subjects 4-12.

9.4 *Compliance with Protocol*

All participants who receive the experimental device will be included in the safety evaluation.

The following events are to be considered sufficient reason for discontinuation of a participant from the study:

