11.1.4 Adverse Event Grading Scales

The severity of all adverse events will be graded as mild (Grade 1), moderate (Grade 2), severe (Grade 3), or potentially life threatening (Grade 4) according to the adverse event grading scale provided below. This grading scale will be used for local adverse events (those related to the cranial site of device administration) and systemic adverse events.

Mild (Grade 1)	Moderate (Grade 2)	Severe (Grade 3)	Potentially Life Threatening (Grade 4)
Symptom is present but does not interfere with activity	Symptom interferes with some activities but does not cause missed attendance at school or work	Incapacitating, unable to attend school or work or perform essential daily activities	Requires emergency room visit or hospitalization

Abnormal vital signs will be graded according to the above severity scale. This grading scale is based on the scale provided in the draft FDA guidance for industry, “Toxicity Grading Scale for Healthy Adult and Adolescent Volunteers Enrolled in Preventive Vaccine Clinical Trials” (April 2005).”

Any "severe" rating for local or systemic events requires the participant to call the study site for evaluation, the study site to notify the Medical Monitor (at the discretion of the investigator), and place comments on the AE page of the CRF that describe the event(s). Any severe adverse event that is deemed possibly, probably or definitely related to the study treatment will invoke a temporary stopping rule for the study to permit evaluation of the event by the SRC (see Section 14.3).

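### Section 11.1.4 grades abnormal vital signs on a scale with no vital-sign values, so a symptom-free reading that needs no emergency or hospital care has no usable grade

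*Protocol*

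**What the plan says.** Section 11.1.4 sets out one four-grade scale for local and systemic adverse events. After the table it adds: "Abnormal vital signs will be graded according to the above severity scale". It then describes the origin of the scale: "This grading scale is based on the scale provided in the draft FDA guidance for industry", naming a draft of April 2005.

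Footnote 2 of the Schedule of Evaluations (Section 3) is worded differently: "Vital signs and laboratory values will be evaluated using the appropriate FDA draft guidance". It does not say which guidance is meant, and no criteria follow.

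Vital signs are part of the physical assessment on Days 0, 3, 7, 42, 180 and 360. Section 11.1.2 lists fever among the systemic events to be watched for and provides a thermometer. Section 10 allows an adverse event to be a sign as well as a symptom, so an abnormal reading can be an event without any complaint from the subject.

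**The concern.** A vital sign is a measured quantity, but the written scale cannot use the measurement. The grade would then reflect how the subject felt, or what care he needed, and not how abnormal the reading was.

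Safety is the primary objective, there is no previous human experience with this plasmid (Section 5.5), and 12 subjects are planned. Grades feed four things:

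- the mild, moderate and severe event rates in 13.2.1;
- the gate in 9.3(a), after the first three subjects;
- the temporary stop in 11.1.4 for related severe events;
- the two stopping rules in 14.3, one for any related serious or severe event and one for three or more related moderate events of the same type.

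With so few subjects, the grade of a single event can decide whether one of these is met. A later analysis plan could not repair this, because site staff assign the grades as events occur and the stopping rules act on them at once.

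**Working it through.** No formula applies, and the protocol states no figure to reproduce. The check reads each anchor against a symptom-free abnormal reading, then traces each route to a trigger.

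**Step 1: the four anchors in 11.1.4.**

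| Grade | Anchor | Contains a vital-sign value? | Can a symptom-free reading meet it? |
|---|---|---|---|
| 1 Mild | "Symptom is present but does not interfere with activity" | No | Not literally, since it needs a symptom; only by default |
| 2 Moderate | "Symptom interferes with some activities but does not cause missed attendance at school or work" | No | No |
| 3 Severe | "Incapacitating, unable to attend school or work or perform essential daily activities" | No | No, because there is no incapacity |
| 4 Potentially life threatening | "Requires emergency room visit or hospitalization" | No | Yes, if that care is required |

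The first three anchors turn on symptoms or function and the fourth on care. A symptom-free reading therefore has nothing between a default Grade 1 and Grade 4.

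**Step 2: is there another vital-sign rule?** The only numeric vital-sign limit in the protocol is the 150/100 blood-pressure exclusion at screening or enrolment. That is an eligibility criterion, not a grade. No temperature threshold for fever is given. Footnote 2 points to guidance without reproducing any criteria.

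**Step 3: routes from a symptom-free reading to a trigger, assuming it is judged at least possibly related.**

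| Route | Needs emergency or hospital care, or meets an SAE criterion | Neither |
|---|---|---|
| Severe (Grade 3) event: 9.3(a), 11.1.4, 14.3 | Closed at Grade 3 | Closed |
| Three or more moderate events: 14.3 | Closed | Closed |
| Grade 4 | Open if emergency or hospital care is required | Closed |
| Serious adverse event: 9.3(a), 14.3 | Open if a Section 10 criterion is met, whatever the grade | Closed |
| Committee judgment of a pattern: 9.3(c) | Open | Open |

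**Step 4: a residual ambiguity.** Sections 9.3(a), 11.1.4 and 14.3 use the word severe, which is the Grade 3 label. Section 13.2.1(b) lists only mild, moderate and severe. A Grade 4 event that is not a serious adverse event, such as an emergency room visit without admission, triggers only if severe is read as Grade 3 or above. The protocol does not say so.

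**Step 5: fever.** Two temperatures of different height get the same grade whenever their effect on function is the same. They can get different grades if the higher one incapacitates the subject. The temperature itself never enters the grade.

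**The case against.** The strongest reply is that dangerous readings are the ones least likely to be missed. Grade 4 needs no symptom. The serious-event arm of 9.3(a) and 14.3 does not depend on grade, and Section 10 counts prolonged hospitalization, life-threatening events and, usually, important medical events needing intervention. The synopsis keeps subjects in hospital for the first week, which is the period the gate reviews, so a reading that prolongs that stay is serious by definition. The committee reviews safety data weekly and can act on a pattern under 9.3(c). All of this stands.

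It defeats two stronger readings that a reader might infer: that a symptom-free reading can never exceed Grade 1 however extreme, and that it cannot reach any stopping trigger. The documents support neither.

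A second reply is that footnote 2 and 11.1.4 may be compatible, since 11.1.4 says its scale derives from draft FDA guidance. That is a fair reading, but it does not close the gap. If footnote 2 means the 11.1.4 scale, there is still no vital-sign value. If it means separate criteria, they are not reproduced and 11.1.4 overrides them in plain words.

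A third reply is that the extent is easily exaggerated. Six visits × 12 subjects gives 72 planned sets of clinic vital signs, of which 5 × 12 = 60 follow the implant visit. These are planned records, not affected ones. It is also not established that daily temperatures are written down: the thermometer is supplied on Day 7, and the second diary card is described as being for unsolicited and serious events. This reply stands too.

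The replies do not reach the middle range. Grade 4 depends on care and not on the value, and for a man already in hospital a need for hospitalization separates cases poorly. An abnormality that is neither trivial nor an emergency still has no defined grade.

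**Conclusion.** The point holds in a limited form. Section 11.1.4 tells the site to grade vital signs on a scale that cannot use them, and footnote 2 of the schedule does not supply the missing criteria. A symptom-free abnormal reading that needs no emergency or hospital care and meets no serious-event criterion is Grade 1 or ungradable whatever its size. It therefore cannot enter the moderate or severe rates, or the gate and stopping rules that use those words. Within that class, severity is understated and unrelated to the measurement.

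The protocol gives no frequency for such readings, so the number affected cannot be stated. The 60 planned post-implant clinic sets show the scale of scheduled collection and are not an estimate of misgraded events.

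The conclusion assumes a literal reading of the four anchors. It does not rely on the contents of the cited guidance, which are not in the protocol. It is worth correcting before the first implant, but it does not mean that extreme readings go unseen.

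**What to change.** Reconcile footnote 2 of the Schedule of Evaluations with Section 11.1.4:

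1. Replace the sentence that sends vital signs to the general scale with a single rule grading them, temperature included, on their measured values.
2. Name the guidance meant in footnote 2 and reproduce in 11.1.4 the vital-sign criteria the sponsor takes from it. If it has none that can be used, say so and state the sponsor's own criteria. No cut-offs are proposed here.
3. Keep the activity-based scale for symptoms.
4. State how vital-sign grades, including a Grade 4 that is not a serious adverse event, enter 9.3 and 14.3. Which rule should apply is for the sponsor and the committee to settle.

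The cost is one sentence, one table and a short clarification. Clinic vital signs are already collected, so no new clinic data are needed. If temperatures taken at home are to be graded, the diary card must ask for the value. The downside is that somewhat more vital-sign abnormalities will reach review.

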10.2 Reporting of Serious Adverse Events

During the study period all SAEs must be reported to the sponsor immediately (within 24 hours). Any SAE occurring from the time of device placement until termination of the study, whether deemed device-related or not, must be reported by facsimile to Agenta immediately (usually within 24 hours) using a SAE Report Form.

SAE Contact Information (Agenta Medical Monitor):

[name].

Cell Phone (24 hours): [contact]

FAX (24 hours): [contact]

Additional contact information for the Medical Monitor is provided in Section 1 of this protocol, "Study Contacts."

The SAE Report must include the Investigator's written medical judgment as to the relation of the event to the experimental device (i.e., "definite/certain", "probable", "possible" or "unrelated"). This initial judgment can be modified later by the investigator, as more information relevant to the SAE becomes available.

Definite/Certain Related is applied to those SAEs which have a temporal relation to the study device and no alternative etiology is present. It must have occurred within a reasonable temporal sequence of the device administration (0 - 7 days), must not be reasonably explained, and must follow a known pattern of response.

Probable Related has a timely relation to the study device and a potential alternative etiology is not apparent (e.g., fever or malaise when no other symptoms suggestive of an illness are present).

Possible Related has a timely relation to the study device; however, a potential alternative etiology exists which may be responsible for the symptom (e.g., fever or malaise when other symptoms are present that suggest another etiology such as urinary tract infection).

Unrelated is applied to those SAEs where evidence exists that the event is definitely related to an etiology other than the study device (e.g., auto accident, or a symptom suggestive of another illness, which is not accepted to be a possible event due to the experimental device).

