13.2 Variables and Timepoints of Measurement

13.2.1 Safety Variables

In-clinic safety evaluation on Days 0, 3, 7, 42, 180, and 360 will be graded for severity and relationship to the study agents and will include:

- a) Rates of SAEs and their relationship to device placement, through 2 years of long-term follow-up.
- b) Rates of local or systemic solicited AEs and their categories (mild, moderate and severe), through Day 360 ± 28 days.
- c) Rates of reported unsolicited AEs, through Day 360 ± 28 days.
- d) Hematologic and biochemical toxicity evaluation following device placement.

Osteogenicity will be evaluated using radiographs and CT scans obtained from participants on Day 0 (baseline, pre-implantation), Day 42 (± 7), 6 weeks after device placement), and Day 180 (± 14) 6 months after device placement).

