14.2 Meeting Schedule/ Adverse Event Review

The SRC will have a scheduled meeting at least once per week during the period of active enrollment and follow-up for each enrolled participant to 42 days. All members of the SRC will review the safety data weekly. Scheduled meetings may be cancelled at the agreement of all three SRC members if there are no safety issues to discuss. The SRC will hold a meeting to review the Day 7 data for the first 3 subjects, and the Day 7 safety data for each subject for the remaining 9 subjects. The SRC will recommend to either continue enrollment or termination of enrollment based on the safety and tolerability of the study product. All AEs that are moderate or mild will be submitted within 7 days from the site to the Study Medical Monitor. SAEs and severe adverse events will be reported within 24 hours after the clinical trial site is aware of the event.

The Medical Monitor will keep and maintain documentation for all SRC meetings with meeting minutes. Agenta personnel will tabulate the data for SRC review.

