14.3 Stopping Rules

Stopping rules will be in place to arrest the enrollment process and suspend all experimental device placement with the occurrence of significant safety event(s). The stopping rules are:

- Any SAE or severe AE that is definitely, probably, or possibly related to the experimental device in the opinion of the investigator or Safety Review Committee.
- Occurrence of 3 or more moderate AEs of the same type that are definitely, probably, or possibly related to the study agent in the opinion of the investigator or Safety Review Committee.

The occurrence of AEs and SAEs will be monitored by the Medical Monitor who will notify the other members of the SRC if a condition is met to institute a stop rule. Enrollment and study agent administration cannot continue after a stop rule has been implemented until the SRC has reviewed the AEs and other subject safety data and made a recommendation to continue the trial as planned, modify the protocol or stop enrollment. The recommendation of the SRC must be reviewed and approved by Agenta.

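### Sections 11.1.4 and 14.2 contradict each other on whether a severe adverse event must be notified, so the stopping rule may be triggered late; one kind of Grade 4 event has no explicit place in the reporting, gate or stopping text

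*Protocol*

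**What the plan says.** **Severe events.** Section 11.1.4 has the participant call the site after a severe rating, and then asks "the study site to notify the Medical Monitor (at the discretion of the investigator"). The next sentence but no other condition links such an event to a temporary halt: a severe AE judged at least possibly related brings one about, pending SRC evaluation.

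Section 14.2 gives two reporting clauses in succession: "All AEs that are moderate or mild will be submitted within 7 days from the site to the Study Medical Monitor", and then "SAEs and severe adverse events will be reported within 24 hours after the clinical trial site is aware of the event". The second names no recipient.

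**Serious events.** Section 10.2 leaves no discretion: "During the study period all SAEs must be reported to the sponsor immediately (within 24 hours"). The contact listed there for SAE reports is the sponsor's Medical Monitor.

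**Stopping.** The first rule in Section 14.3 is "Any SAE or severe AE that is definitely, probably, or possibly related to the experimental device", in the opinion of the investigator or the SRC. AEs and SAEs are "monitored by the Medical Monitor who will notify the other members of the SRC if a condition is met to institute a stop rule".

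**Grades.** The top of the four-grade scale in Section 11.1.4 reads "severe (Grade 3), or potentially life threatening (Grade 4"). Grade 4 is defined by an emergency room visit or hospitalization. Section 13.2.1(b) lists "Rates of local or systemic solicited AEs and their categories (mild, moderate and severe), through Day 360 ± 28 days".

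**The concern.** Safety is the primary objective, the protocol reports no previous human experience with this plasmid approach, and a single related severe AE is meant to suspend further implantation. That control depends on the event reaching the Medical Monitor, whom Section 14.3 makes responsible for telling the rest of the SRC. If the notice is optional in one section and required within a day in another, site staff can follow the protocol and still delay it.

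What is at stake is the timing of the stop and the independence of the causality judgment. Section 14.3 allows the SRC to form its own opinion on relatedness, but the SRC can do so only once it knows of the event. Where the investigator considers an event unrelated and uses the discretion not to notify, that second opinion may come late.

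The grading scale adds a smaller ambiguity. The label *severe* belongs to Grade 3 alone, yet the operating text uses only mild, moderate, severe and SAE. It is not stated whether *severe* is meant to include the grade above it.

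**Working it through.** No arithmetic applies. The point does not use the sample size table in Section 13.1 or any other figure of that kind. The check sets the passages side by side for each class of event.

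| Class of event | Reporting route stated | Stop trigger stated |
|---|---|---|
| Mild or moderate | Medical Monitor within 7 days (10.1, 14.2) | Three or more related moderate AEs of one type (14.3) |
| Severe (Grade 3), not serious | 11.1.4: investigator's discretion, no time limit. 14.2: within 24 hours, recipient not named | One related event (11.1.4, 14.3) |
| Grade 4 with inpatient admission or prolonged stay | SAE under Section 10, so 24 hours to the sponsor (10.2) | One related event, as an SAE (14.3) |
| Grade 4, emergency room only, judged an important medical event | Usually an SAE under Section 10, so as above | As above |
| Grade 4, emergency room only, not so judged | Not named | Not named |

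**Row 2, the contradiction.**
1. The 24-hour sentence in Section 14.2 follows directly on the sentence that sends mild and moderate AEs to the Medical Monitor. The Medical Monitor is therefore its natural recipient, although this is an inference.
2. On that reading, Sections 11.1.4 and 14.2 govern the same notice, and one makes optional what the other requires.
3. Section 14.3 needs that notice, because the Medical Monitor is the person who alerts the SRC.
4. Section 10 gives no route for a severe AE that is not serious. Staff working only from Sections 10 and 11 would find mild events compulsory to submit and severe events discretionary.

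**Rows 3 to 5, Grade 4.**
1. Inpatient hospitalization is a listed SAE criterion. An emergency room visit alone is not.
2. Section 10 confines *life-threatening* to an actual risk of death at the time of the event, so the label *potentially* life threatening does not make an event serious by itself.
3. The clause on important medical events can bring an emergency-room-only event in, but only by judgment.
4. What remains is row 5. The enrollment gate in Section 9.3 uses the same terms (SAE or severe AE), so this event is not named there either.

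**Backstops.** The Principal Investigator is one of the three SRC members (14.1). All members review safety data weekly, and the SRC reviews Day 7 data for the first three subjects and for each of the remaining nine (14.2).

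**The case against.** The strongest reply is that the rule still operates. Section 11.1.4 itself ties a related severe AE to a halt without making that depend on the notice. Section 14.3 can be met on the investigator's opinion, and the Principal Investigator sits on the SRC and prepares the device at this single site. Weekly data review is stated separately from the meetings, so cancelling a meeting, which needs the agreement of all three members and the absence of safety issues, does not cancel the review. It can also be argued that the discretion concerns only a participant's own rating before the site has evaluated it.

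Most of this stands, and it limits the effect to delay. The last argument is possible, but the text does not say that the discretion ends after evaluation. The backstops are also partial: the data for SRC review are tabulated by sponsor personnel, and a view that there is nothing to discuss assumes that the event has been passed on.

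Four stronger readings are tempting and are not supported:
- **The stopping rule can fail altogether.** The points above tell against this.
- **Up to nine further implants are at risk** (12 − 3 = 9). This would need an event in the first three subjects that emerged after the gate had cleared, followed by all remaining implants before it surfaced. An event in subject 4 leaves at most 12 − 4 = 8. No accrual rate is stated from which to judge either figure.
- **SRC meetings lapse at Day 42.** Section 14.2 schedules them through active enrollment and each subject's follow-up to 42 days, which on the natural reading covers the whole period in which an implant could be suspended.
- **Grade 4 is unprotected and untabulated.** Admitted cases are SAEs. Section 13.3.1 tabulates AEs by severity without limiting the grades, and Section 13.2.1(b) concerns solicited events only.

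**Conclusion.** The protocol is wrong as written on one point: Sections 11.1.4 and 14.2 give incompatible instructions for notifying severe AEs, and Section 14.3 depends on the outcome. The effect is confined to severe (Grade 3) AEs that are not serious. For these, the stopping rule and the SRC's own causality opinion could be triggered late, and a further subject could be treated in the meantime. With weekly review working as described, the delay should be of the order of a week. It could be longer only if the event does not reach the reviewed data.

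The Grade 4 gap is real but narrow. It covers an emergency room visit without admission that is not judged an important medical event, and only if *severe* is read literally as Grade 3.

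The conclusion assumes that the Medical Monitor is the intended recipient of the 24-hour report in Section 14.2. If someone else is intended, the direct contradiction weakens, but Section 14.3 would then depend on a notice that no section requires for these events. Because the conflict lies in the trigger for the trial's main safety control and wording alone can remove it, it should be resolved.

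**What to change.** 1. Reconcile Section 11.1.4 with Sections 14.2 and 14.3 so that one consistent statement says whether severe AEs are reported, to whom, and within what time. Name the recipient in Section 14.2. If the discretion in Section 11.1.4 is meant to apply only before the site's evaluation, say so.
2. State how Grade 4 maps to the reporting text (10.1, 14.2), the enrollment gate (9.3), the stopping text (11.1.4, 14.3) and the severity categories in Section 13.2.1(b).

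Which notification and stopping rule applies is a clinical decision for the sponsor. The request is only that the sections agree.

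The cost is wording in these sections. No visits, procedures or staff are added. Depending on the rule chosen, there may be a few more notifications.
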